8.3.2 Scan Interpretations

⁶⁸Ga-PSMA-11 PET/CT images will initially be interpreted by a board certified nuclear medicine physician or a board-certified radiologist experienced in reading PET/CT at the time of the imaging study at the institution that the study is being performed. These interpretations will be made available to the treating physician and will become part of the patient's electronic record. These interpretations will however not be used for final evaluation.

8.3.3 Central Data Analysis

Anonymized coded patient information (case report forms) will be captured in a central REDCap database hosted at the University of California at San Francisco (UCSF).

Anonymized and de-identified imaging data will be uploaded to a central website hosted at the Clinical Trials Network (CTN). PET data will be interpreted by three different readers in a random order at separate reading sessions. Cross sectional imaging (CT) obtained with the ⁶⁸Ga PSMA-11 PET will be available as anatomic correlate.

Central Read Interpretation: Final reads by the central read physicians for each subject will be interpreted as positive or negative for the presence of disease in the regions defined in section 8.2.1 (see table).

Reader Positivity and Negativity Definition: Regions of suspected disease will be graded on a two-point scale by each reader (0=Negative or 1=Positive). A region will be judged as positive if at least one lesion in this region is visually positive. Criteria for visual interpretation is described in section 8.3.3.

Reader Training: ⁶⁸Ga PSMA-11 PET/CT reading training set and guides will be provided and completion of this training will be required for all central review readers.

Case report forms will be provided to the FDA for review, when requested.

8.3.4 Analysis of Primary Endpoints

Primary endpoint: PPV on a per-patient basis of ⁶⁸Ga-PSMA-11 PET for detection of prostate cancer confirmed by histopathology will be calculated and reported along with the corresponding two-sided 95% confidence intervals. The confidence intervals will be constructed using the Wilson score method.

a) Imaging interpretation ⁶⁸Ga-PSMA-11 PET:

PET images will initially be interpreted by a board certified nuclear medicine physician or a board certified radiologist experienced in reading PET at the time of the imaging study at the University of Michigan. These interpretations will not be used for final evaluation. Upon request, anonymized ⁶⁸Ga-PSMA PET/CT imaging data are sent to the FDA for further review.

Visual interpretation:

Regions of suspected disease will be graded on a two-point scale by each reader (0=Negative or 1= Positive). A region will be judged as positive if at least one lesion in this region is visually positive.

- i) Lymph nodes will be considered positive if the ⁶⁸Ga-PSMA-11 uptake is focal and greater than blood pool (adjacent or mediastinal blood pool). Pelvic lymph nodes will be subclassified according to their localization as follows: R/L obturator, R/L external iliac, R/L internal iliac and other (total of 7 subgroups).
- ii) Visceral lesions will be considered positive if the ⁶⁸Ga-PSMA-11 uptake is focal and greater than physiologic background activity of the involvement organ or anatomic site.

- iii) Bone lesions will be considered positive if the ^{68}Ga -PSMA-11 uptake is focal and greater than physiologic bone marrow.
- iv) Prostate bed and prostate lesions will be considered positive if the ^{68}Ga -PSMA-11 uptake is focal and greater than physiologic background activity of the involvement organ or anatomic site.

b) Follow-up Imaging:

All patients are expected to be followed up as part of clinical care within 3-12 months with conventional imaging (dedicated CT, MRI and/or bone scan). Interpretation of follow-up imaging will be performed by local read. The follow-up conventional imaging should be the same modality/modalities as the initial staging work-up to allow reproducible and accurate comparisons.

^{68}Ga -PSMA-11 PET positive findings will be validated as true or false positive as outlined in more detail below. False negative ^{68}Ga -PSMA-11 PET findings may be determined based on biopsies obtained from lesion identified on conventional imaging that are negative on ^{68}Ga -PSMA-11.

Rationale for applied response criteria:

RECIST 1.1 defines a size decrease of at least 30% as response (either partial or complete), while an increase of at least 20% is considered progressive disease ^{42,43}. The decline of serum PSA of 50% or more is a commonly used criterion for treatment response following systemic treatment of metastatic prostate cancer ⁴⁴⁻⁴⁶.

Following the ^{68}Ga -PSMA-11 PET/CT scan, focal therapies of metastatic lesions may be performed without systemic treatment. Therefore, anatomic size variations can be suitable endpoints in absence of histological verification. In patients with solitary lesions, PSA reductions following focal treatment may indicate a true positive scan finding even in absence of significant size changes.

^{68}Ga -PSMA-11 PET validation based on follow-up imaging:

- i) Lymph nodes will be assessed by change in size. ^{68}Ga -PSMA-11 positive lymph nodes will be considered:
 - (1) True positive:
 - If on follow-up imaging within 3-12 months, lymph nodes seen on CT or MRI decrease by more than 30% (for patients undergoing systemic treatment of focal therapy at this site) or increase by more than 20% in short axis diameter (with a minimum of 3 mm in change in size).
 - If patients with solitary lymph node regions show a decrease of PSA by greater than 50% after targeted treatment (i.e. external beam radiation) and the lymph nodes do not change in size (less than 30% decrease or less than 20% increase in short axis diameter).
 - (2) False positive:

- If on follow-up imaging within 3-12 months, sites of initial ⁶⁸Ga-PSMA-11 positive lymph node lesions seen on CT or MRI decrease by more than 30% *without* systemic therapy or focal therapy at this site.

- If ⁶⁸Ga-PSMA-11 positive lymph node lesions do not meet the criteria for above false positive or true positive findings.

ii) Visceral lesions (non-lymph node soft tissue or organ) will be assessed by change in size. ⁶⁸Ga-PSMA-11 positive visceral lesions will be considered:

(1) True positive:

- If on follow-up imaging within 3-12 months, visceral lesions seen on CT or MRI decrease by 30% (for patients undergoing systemic treatment of focal therapy at this site) or increase by 20% in largest diameter.

- If patients with solitary visceral metastasis show a decrease of PSA by greater than 50% after targeted treatment (i.e. external beam radiation) and lesions do not change in size (less than 30% decrease or 20% increase in largest diameter).

(2) False positive:

- If on follow-up imaging within 3-12 months, sites of initial ⁶⁸Ga-PSMA-11 positive lymph node lesions seen on CT or MRI decrease by more than 30% *without* systemic therapy or focal therapy at this site.

- If ⁶⁸Ga-PSMA-11 positive lymph node lesions do not meet the criteria for above false positive or true positive findings.

iii) ⁶⁸Ga-PSMA-11 positive bone lesions will be considered:

(1) True positive:

- If there was a corresponding positive sclerotic lesion on the CT portion of the ⁶⁸Ga-PSMA-11 PET.

- If there is focal uptake seen on the baseline bone scan performed within one month of ⁶⁸Ga-PSMA-11 PET.

- If there is a lesion noted on the initial MRI performed within one month of ⁶⁸Ga-PSMA-11 PET.

- If within 12 months follow-up CT demonstrates development of sclerosis.

- If within 12 months follow-up MRI demonstrates a new bone lesion.

- If within 12 months follow-up bone scan demonstrates new focal uptake.

(2) False positive:

- If ⁶⁸Ga-PSMA-11 positive bone lesions do not meet the criteria for true positive findings.

iv) ⁶⁸Ga-PSMA-11 positive prostate bed and prostate lesions will be considered:

(1) True positive:

- If on follow-up imaging within 12 months, lesions seen on CT or MRI decrease by 30% (for patients undergoing systemic treatment of focal therapy at this site) or increase by 20% in largest diameter.
- If patients with prostate bed lesions show a decrease of PSA by greater than 50% after targeted treatment (i.e. external beam radiation) and lesions do not change in size (less than 30% decrease or 20% increase in largest diameter).

(2) False positive:

- If on follow-up imaging within 3-12 months, sites of initial ⁶⁸Ga-PSMA-11 positive lymph node lesions seen on CT or MRI decrease by more than 30% *without* systemic therapy or focal therapy at this site.
- If ⁶⁸Ga-PSMA-11 positive lymph node lesions do not meet the criteria for above false positive or true positive findings.

c) Histopathology/Biopsy:

- i) Localization of lesions for histopathology/biopsy will be a classified according to the regions in table 1.
- ii) ⁶⁸Ga-PSMA-11 positive findings are aimed to be confirmed by histopathology/biopsy if clinically feasible.
- iii) Histopathological procedures and biopsies will be performed as clinically indicated and as per institutional protocol.

(1) Positive HP/Biopsy: Confirmed sites of metastatic or tumor involvement by histopathology/biopsy will be discussed with the responsible physician/surgeon.

(2) Negative Biopsy: Patients with suspected tumor recurrence on ⁶⁸Ga-PSMA-11 PET with negative histopathology/biopsy will be handled as outlined below:

(a) Lymph nodes:

- For patients undergoing nodal dissection: Patients will be rescanned with dedicated CT or MRI to determine if the suspicious ⁶⁸Ga-PSMA-11 positive node was removed.
 1. If ⁶⁸Ga-PSMA-11 positive lymph node is still present, a repeat biopsy can be pursued if clinically feasible and applicable, or follow-up using imaging as described above will be performed.
 2. If the corresponding node was removed, then this will be considered a False Positive.
- For patients undergoing needle biopsy: Images of the procedure will be reviewed to determine if the correct node was biopsied.
 1. If the correct node was biopsied, then a negative biopsy will be considered a False Positive.

2. If the incorrect node was biopsied, then follow-up imaging as described above will be performed.
- (b) Bone lesions: Given the high rate of false negative biopsies for osseous metastases in patients with prostate cancer, patients with negative bone biopsies of PSMA PET positive lesions will be further evaluated:
 - If pathology demonstrates an alternative diagnosis that is known to be PSMA positive (eg Renal Cell Carcinoma metastases, Paget's disease), then this will be considered a False Positive.
 - If pathology is indeterminate, then follow-up imaging as described above will be performed to determine if the lesion is a True Positive or False Positive.
 - Additionally, a repeat ⁶⁸Ga-PSMA-11 can also be obtained, as allowable, in addition to repeat conventional imaging (CT and/or MRI) in cases of negative biopsy to determine if the biopsy was true negative or false negative.
- (3) Although not routinely performed during standard practice, immunohistochemical staining for PSMA of tumor specimens (primary and lymph node metastases) may be performed, although not required.

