Current standard imaging of early recurrent prostate cancer is insufficient. Accurate detection of tumor locations is essential as the clinical management varies from active surveillance to targeted local to systemic therapy⁷. Per NCCN guidelines at the time of biochemical recurrence, imaging is performed to detect and characterize the disease to determine treatment or guide change in management. Imaging can evaluate anatomic or functional parameters and the following imaging is recommended as standard techniques at this time-point:

- Imaging is performed for the detection and characterization of disease to select treatment or guide change in management.
- Anatomic imaging techniques include plain film radiographs, ultrasound, CT, and MRI.
- Functional imaging techniques include radionuclide bone scan, PET, and advanced MRI techniques such as spectroscopy and diffusion-weighted imaging (DWI).

More specifically, Current U.S. guidelines recommend either a radionuclide bone scan, abdominopelvic CT, multi-parameter MRI or – where available - choline PET/CT for patients with rising PSA or clinical symptoms⁷. The probability of a positive bone scan is reported to be <5% with a serum PSA level of <7 ng/mL. A CT scan will only be positive in 11–14% of patients

with BCR⁸. Additionally, in a study with 132 patients, the mean PSA level of patients with a positive CT scan was 27.4 ng/ml⁸.

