Earlier detection of macroscopic metastatic disease in castration sensitive prostate cancer by novel highly sensitive molecular imaging techniques could lead to detection of prostate cancer metastases at lower tumor burdens presenting as oligometastatic prostate cancer rather than as diffusely metastatic prostate cancer. While the definition of oligometastatic disease varies, the addition of locoregional ablative therapies directed at sites of macroscopic disease to conventional systemic therapy has shown promise with respect to delaying progression of disease in other cancer types. A recent randomized trial in oligometastatic non-small cell lung cancer demonstrated that the addition of locoregional therapy to systemic therapy improved progression-free survival³⁶. More importantly, the addition of locoregional therapy doubled the time to the appearance of disease at new sites, indicating that the overall natural history of the disease was altered.

In prostate cancer, multiple studies suggest a benefit from locoregional therapy in oligometastatic disease. Given that maximally effective use of locoregional therapy requires accurate knowledge of disease extent, further investigation of the clinical impact of highly sensitive molecular imaging is critical. Incorporation of additional focal or targeted therapeutic modalities could be valuable in this patient population, but is currently limited by the low sensitivity of standard imaging modalities. The STOMP trial is an ongoing randomized phase study utilizing metastases-directed therapy with either surgery or stereotactic body radiotherapy, with less than or equal to 3 metastases defining oligometastatic disease diagnosed on choline PET/CT³⁷. The ORIOLE trial is also an ongoing randomized phase II study assessing the efficacy of stereotactic ablative radiotherapy in patients who have failed primary treatment and have developed oligometastatic disease with three or fewer bone metastases³⁸.

Based on the available data, it is evident that the full extent of metastatic disease patients with biochemically recurrent prostate cancer is frequently underestimated on conventional imaging when compared to advanced molecular imaging techniques. Importantly, the utility of ^{68}Ga -PSMA PET/CT to identify such metastatic lesions earlier prior their appearance on standard imaging has not yet been evaluated in the randomized setting.

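### The follow-up rules for nodes, visceral lesions and prostate bed do not say how to score a PET-positive site where a lesion first becomes visible at follow-up; the bone rule does

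*Combined protocol and SAP*

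**What the plan says.** Section 8.3.4 b) classifies each PET-positive finding from follow-up imaging, separately by lesion type.

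For lymph nodes (i) there are two true-positive routes. The first is a size change: "If on follow-up imaging within 3-12 months, lymph nodes seen on CT or MRI decrease by more than 30" per cent under treatment, "or increase by more than 20% in short axis diameter (with a minimum of 3 mm in change in size"). The second is biochemical: "If patients with solitary lymph node regions show a decrease of PSA by greater than 50% after targeted treatment", on condition that "the lymph nodes do not change in size (less than 30% decrease or less than 20% increase in short axis diameter"). A residual bullet then makes a node a false positive if "positive lymph node lesions do not meet the criteria for above false positive or true positive findings".

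Visceral lesions (ii) and prostate-bed lesions (iv) follow the same pattern, with 30% and 20% thresholds on largest diameter and a PSA route that also requires no size change. Their false-positive bullets repeat the lymph-node text.

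Bone (iii) differs. Among its true-positive criteria is "If within 12 months follow-up MRI demonstrates a new bone lesion", alongside new sclerosis on CT and new focal uptake on bone scan.

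These classifications feed the composite per-patient and per-region PPV in 8.3.5, item 1. The primary PPV rests on patients with histopathology (8.3.1). Follow-up imaging is read locally (5.3 and 8.3.4 b).

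**The concern.** A percentage change needs a baseline diameter, and a site positive on PET alone has none. If a node or mass later appears exactly there, follow-up supports the PET finding, yet no true-positive bullet in i, ii or iv describes that course.

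This matters because early detection is part of the case for the tracer: section 1.2 speaks of its use to "identify such metastatic lesions earlier prior their appearance on standard imaging". A reference standard that may count such a case as an error works against the property the study wants to show. It also gives region 4 (bone) a route to confirmation that regions 1 to 3 do not clearly have, although 8.2.1 claims adequate power for region-specific tests in the pooled sample.

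**Working it through.** The plan gives no figure on this point, so the check is textual, followed by a labelled illustration.

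**Step 1. The four rules side by side (8.3.4 b).**

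| Rule | Size route | PSA route | New finding accepted | Residual false-positive bullet covers |
|---|---|---|---|---|
| i Nodes | decrease >30% (treated) or increase >20%, minimum 3 mm | solitary region, fall >50%, no size change | not mentioned | nodes |
| ii Visceral | decrease 30% (treated) or increase 20% | solitary lesion, fall >50%, no size change | not mentioned | nodes only, as written |
| iii Bone | none | none | yes (CT, MRI, bone scan) | bone |
| iv Prostate bed | decrease 30% (treated) or increase 20% | fall >50%, no size change | not mentioned | nodes only, as written |

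**Step 2. A test case.** Take a PET-positive site with nothing visible at baseline and an 8 mm lesion there at follow-up.

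- Node, size route: the absolute change is 8 − 0 = 8 mm, which passes the 3 mm minimum. The percentage is (8 − 0)/0, which is undefined.
- Node, PSA route: it requires no size change, so a newly visible node does not fit.
- Node, strict result: no true-positive bullet is met, so the residual bullet gives false positive.
- Node, lenient result: a reader who counts nothing-to-8 mm as more than 20% growth records true positive.
- Visceral or prostate bed: no true-positive bullet clearly applies, and the residual bullet speaks of nodes. The result is not stated.
- Bone, with a new lesion on MRI: true positive.

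**Step 3. How much rests on follow-up imaging.** Section 8.2.1 reports biopsies of PET-positive lesions in 13 of 316 evaluable subjects: 13/316 = 4.1%. At that rate, follow-up rather than histopathology carries most of the composite standard.

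**Step 4. Illustration of the effect.** Let P be the PPV if every finding were classified correctly, and f the share of truly malignant PET-positive findings that lack a baseline correlate and newly appear. Both are assumptions.

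- Scored false positive: observed PPV = P × (1 − f). With P = 0.75 and f = 0.10: 0.75 × 0.90 = 0.675.
- Left out as unclassifiable: P × (1 − f)/(1 − P × f) = 0.675/(1 − 0.075) = 0.730.

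| f | P = 75%: false positive | P = 75%: left out | P = 90%: false positive | P = 90%: left out |
|---|---|---|---|---|
| 5% | 71.3% | 74.0% | 85.5% | 89.5% |
| 10% | 67.5% | 73.0% | 81.0% | 89.0% |
| 20% | 60.0% | 70.6% | 72.0% | 87.8% |
| 30% | 52.5% | 67.7% | 63.0% | 86.3% |

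Under the lenient reading there is no loss.

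**The case against.** The strongest reply is that this is an ambiguity in a secondary endpoint and not a closed door. Much of that stands.

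- A reader might infer that percentage change is the only way to true positive. It is not. Rules i, ii and iv each have a PSA route, which in iv is not limited to solitary disease, and histopathology (8.3.4 c) is a further route. The secondary objective in 2.2 also names clinical follow-up. The PSA route covers a treated lesion that stays invisible, so the gap is confined to lesions that emerge on CT or MRI within the window.
- A reader might infer that the lesion must have been visible at baseline. The text says only that it is seen on CT or MRI. The baseline reading is supported by the heading criterion of change in size and by the request in 8.3.4 b) for the same modality as the initial work-up, but it remains an inference.
- A reader might infer a false-positive default throughout regions 1 to 3. It is written for nodes only; in ii and iv the outcome is simply missing.
- A reader might size the effect from section 1.2: "A CT scan will only be positive in 11–14% of patients" with biochemical recurrence. That is patient-level CT positivity, not the share of PET-positive lesions with a baseline correlate. Small nodes can be measurable on the CT acquired with the PET without having been called positive.
- Bone also accepts a baseline correlate alone as true positive, so region 4 would still differ from the others after any repair here.

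What the reply does not remove is the combination of a rule open to two readings, a written false-positive default for nodes, and local reading of follow-up. Together these allow identical events to be scored in opposite ways in pooled data.

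**Conclusion.** The gap is real and worth closing. Rules i, ii and iv contain no criterion for a lesion that newly appears at a PET-positive site, whereas rule iii does. Strict application to nodes scores such disease as false positive and biases the secondary composite PPV downward. For visceral and prostate-bed lesions the documents give no outcome.

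The size cannot be derived from the documents. The fall from 75% to 67.5% rests on an assumed true PPV, an assumed 10% of true lesions affected, strict scoring everywhere and otherwise correct classification.

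A reader might conclude that the primary result is compromised. The documents do not support that: the primary PPV is based on histopathology and is touched only where 8.3.4 c) returns a negative or indeterminate biopsy to follow-up imaging. For the bone lesions returned that way, rule iii already accepts new findings.

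**What to change.** In 8.3.4 b), add one true-positive bullet to each of i, ii and iv: *no correlate on baseline CT/MRI and a new lesion at the PET-positive site on follow-up CT/MRI*. Keep each rule's existing window: 3-12 months for i and ii, within 12 months for iv. Apply the existing 3 mm minimum to nodes only, since ii and iv have none. Correct the false-positive bullets in ii and iv so that they name visceral and prostate-bed lesions.

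The secondary endpoints are analysed centrally over 1,500 patients (2.3.2), and endpoints were aligned across institutions for pooling (1.1). The wording should therefore go into the pooled criteria, not into one site's protocol alone, and before lesions are classified. Any findings already classified would need to be checked against it.

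The cost is a few lines of text and agreement between sites. No new procedures or patients are needed, because 5.3 already provides for collecting follow-up reports and images. The downside is that an occasional incidental benign lesion newly visible at the PET-positive site may count as true positive.

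### In the lymph node rules, the 3 mm minimum change applies to the size criterion but not to the PSA criterion's definition of no change, so some nodes confirmed by a PSA fall default to false positive

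*Combined protocol and SAP*

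**What the plan says.** The relevant rules are the lymph node rules in section 8.3.4 b) i), under validation by follow-up imaging.

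- **Size criterion, true positive.** A node under treatment shrinks by more than 30%, or a node grows by more than 20% in short axis, on CT or MRI at 3-12 months. A parenthesis directly after the growth threshold adds "with a minimum of 3 mm in change in size".
- **PSA criterion, true positive.** Patients with "solitary lymph node regions show a decrease of PSA by greater than 50% after targeted treatment", provided that the nodes "do not change in size (less than 30% decrease or less than 20% increase in short axis diameter"). No millimetre figure appears here.
- **False positive, first criterion.** Shrinkage of more than 30% without systemic therapy or focal therapy at the site.
- **False positive, catch-all.** The case in which "positive lymph node lesions do not meet the criteria for above false positive or true positive findings".

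The rationale earlier in 8.3.4 b) explains the PSA criterion: in patients with solitary lesions, "PSA reductions following focal treatment may indicate a true positive scan finding even in absence of significant size changes".

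Section 8.3.5, item 1, uses follow-up imaging together with histopathology as the reference for the per-patient and per-region PPV. Section 2.3.2 places this secondary endpoint in the pooled population of 1,500. The primary PPV uses histopathology (sections 8.2.1 and 8.3.1).

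**The concern.** An absolute minimum guards against reading measurement error as change, and that is reasonable. A change too small to count as change should then count as no change, which is the situation the PSA criterion was written for. As drafted, the two criteria draw the line in different places. A node between the two lines is too little changed for the size criterion and too much changed for the PSA criterion, so it drops to the catch-all.

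The nodes affected are ones that the plan would otherwise accept as confirmed on the PSA fall. Each one that drops through moves from true positive to false positive, so the error runs in one direction. It also bears on a reference standard that depends heavily on imaging: section 8.2.1 reports biopsies of PSMA-positive lesions in only 13 of 316 evaluable subjects.

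**Working it through.** The plan states no figure to reproduce. The check applies the rules as written.

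**Inputs (section 8.3.4 b) i)).** Shrinkage threshold 30%, growth threshold 20%, minimum change 3 mm, PSA fall above 50% after targeted treatment of a solitary node region. The node sizes below are illustrations, since the documents give none.

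**Where the gap lies.** For baseline short axis b in mm, a node meets neither true-positive criterion, despite the PSA fall, when:

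- shrinkage: 0.30 × b < change < 3 mm. This is possible only if b < 3/0.30 = 10 mm.
- growth: 0.20 × b < change < 3 mm. This is possible only if b < 3/0.20 = 15 mm.

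For b = 8 mm, the shrinkage gap is 2.4 to 3 mm (follow-up size between 5.0 and 5.6 mm) and the growth gap is 1.6 to 3 mm (between 9.6 and 11 mm). For b = 6 mm, the shrinkage gap is 1.8 to 3 mm. For b = 5 mm, it is 1.5 to 3 mm.

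**Classification with the PSA fall present and the minimum applied to both directions:**

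| Short axis (mm) | Change | Size criterion | PSA criterion | Class |
|---|---|---|---|---|
| 8 to 8 | 0% | no | yes | true positive |
| 8 to 6 | -25%, 2.0 mm | no | yes | true positive |
| 8 to 5.4 | -32.5%, 2.6 mm | no (under 3 mm) | no (over 30%) | false positive |
| 8 to 5 | -37.5%, 3.0 mm | yes | not needed | true positive |
| 8 to 10 | +25%, 2.0 mm | no (under 3 mm) | no (over 20%) | false positive |
| 8 to 11 | +37.5%, 3.0 mm | yes | not needed | true positive |

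As shrinkage increases, the class runs true, true, false, true.

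**Minimum applied to increases only.** The 8 to 5.4 mm node becomes true positive on size, so the shrinkage gap closes. The 8 to 10 mm node remains false positive.

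**Direction of the effect.** PPV = TP/(TP + FP). If k of N classified positives move from TP to FP, PPV falls by k/N. For the per-patient PPV, this assumes that no other finding in the patient is validated as true positive. The documents give no node-size distribution, so k cannot be computed.

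**After the change proposed below.** With the PSA fall, 8 to 5.4 mm and 8 to 10 mm both become true positive. A node at exactly 30% (10 to 7 mm) currently meets neither criterion, because one says more than and the other less than. It is also settled.

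**The case against.** The strongest objection is that the parenthesis with the 3 mm minimum follows the growth wording and may qualify growth alone. The shrinkage gap would then not exist. This stands as an open reading. The words refer to change in size generally, so applying them to both directions is at least as natural, but the text does not settle it. The growth gap survives either way.

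A second objection is that the or in the PSA criterion, read literally, admits any shrinkage, since a shrinking node has grown by less than 20%. That would empty the condition and contradict the requirement of no change in size.

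Three stronger readings are tempting, and the documents do not support them:

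- A reader might infer that treated small nodes that shrink are generally classed as false positive. The reversal needs a solitary node region, targeted treatment, a PSA fall above 50%, a baseline under 10 mm, and shrinkage over 30% but under 3 mm. Without the PSA fall, the unchanged node is false positive too, so nothing is reversed.
- A reader might count an untreated node that grows from 6 to 8 mm as the same fault. It cannot reach the PSA criterion, which requires targeted treatment. That case is the 3 mm guard at work, followed by the catch-all.
- A reader might infer that the primary endpoint is compromised. Section 8.3.4 c) sends a node back to follow-up imaging only after a negative biopsy or dissection in which the PSMA-positive node was left in place or the wrong node was sampled. A negative result from the correct node is a false positive directly.

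**Conclusion.** The two true-positive criteria for nodes do not fit together, and no other section repairs this. The node rules for follow-up imaging have no indeterminate class. The visceral and prostate-bed rules carry no millimetre minimum, so this mismatch is specific to nodes. The result conflicts with the plan's own rationale for accepting a PSA fall when size change is not significant.

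The growth gap (baselines below 15 mm) holds on either reading of the minimum. The shrinkage gap (baselines below 10 mm) holds only if the minimum also covers decreases. The consequence is a downward bias in the composite-reference nodal and per-patient PPV. A reader might want to express this in percentage points, but any such figure would only restate an assumed share of affected nodes. The point is worth correcting because the wording is wrong as it stands and the repair is small. A large effect has not been shown.

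**What to change.** Make two changes in section 8.3.4 b) i):

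1. State whether the 3 mm minimum applies to both decreases and increases, or to increases only.
2. Reword the PSA criterion so that, with its PSA and treatment conditions unchanged, it applies whenever the node does not meet the size criterion, including the 3 mm minimum. A change under 3 mm then counts as no change.

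The same wording should be agreed for the pooled central analysis, because section 1.1 aligns endpoints across institutions for data sharing.

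The cost is a small rewording of the reference standard during an unblinded study that already has 316 evaluable subjects. It has to be agreed across sites, and nodes already classified must be re-derived from recorded measurements, which assumes that short-axis values were kept. The number of nodes that change class should be reported. No new data collection or staff is needed.

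A separate not-evaluable class is not proposed. For untreated nodes that shrink by more than 30% but under 3 mm, it would conflict with the first false-positive criterion. Removing only would-be false positives from the denominator could also only raise PPV.
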